## Study Protocol

Official Title: Family Empowerment for Enhanced  
Development (Project FEED)

ClinicalTrials.gov ID (NCT number): NCT03641716

Protocol Date: 5/14/2020

**Scientific Background:** Despite increased public awareness, childhood obesity rates have nearly tripled over the past four decades and remain high. Child onset obesity takes a toll on all aspects of health, as it increases risk for poor school performance, social isolation, Type 2 diabetes, sleep apnea and predicts obesity as an adult. Low-income preschoolers are disproportionately affected; approximately 15% of preschoolers from low-income families are obese prior to their fifth birthday, as compared with 8% observed in the general population. Building preventative healthy habits during early childhood is crucial, as rates of obesity increase among school-age children. While it is clear that genetics and social factors, such as income, ethnicity, and minority status, influence obesity, poor nutrition and lack of physical activity are recognized as the primary causal mechanisms. Therefore, the World Health Organization has called for interventions to improve nutrition and physical activity early in life. Specific to building healthy dietary variety, early intervention is vital because children are more receptive to trying new foods prior to age five, and early food preferences in young children are likely to carry forward into adulthood. Partnering with families to build healthy dietary habits early is a pivotal component of obesity prevention efforts. Our study will focus on this outcome, promoting healthy nutrition, among low-income preschoolers.

Because parents are responsible for the timing, setting, and foods offered during child meals, they hold the key to shifting the mealtime routines of young children. Embedding parent-mediated intervention strategies into a child's daily natural environment has been widely endorsed as best practice, yet evidence to support current methods of parent-training in the home is limited. Innovative parent-training strategies are needed, as parents of young children report difficulty incorporating new skills into established daily routines. Our pilot data support the premise that training parents to create a mealtime environment enriched with healthy role models and repeated exposure to a variety of foods can improve child nutrition. We predict that these behavioral and environmental changes are more likely to persist when routines are family-centered and practiced in the natural environment.

Motivational interviewing and anticipatory guidance have been used to change home routines of preschoolers. While these techniques have improved routines related to sleep and television watching, changes in mealtime have not been observed and effects on child nutrition are unclear. Many of these studies offer disparate strategies to support healthy weight management without connecting these strategies to existing family routines or considering unique family dynamics. These strategies can be modified to meet the needs of each family, but this opportunity is often overlooked. This is particularly important for low-income parents who are likely to be focused on surviving life stressors, and have limited resources to independently solve these problems. Additionally, these interventions are delivered in a variety of formats (face-to-face, mail, phone calls, text messages), some of which lack the capacity for individualized problem solving to overcome barriers. While parents perceive mailed and phone-based intervention-delivery as convenient, they may lack the structure and support required for long-term behavior change.

Furthermore, few studies include formal follow-up procedures related to successes and failures implementing new routines or strategies. Our prior research highlights the importance of individualized feedback during routine family activities. In a small pilot trial of the Mealtime PREP intervention, we found that those children whose parents received feedback during actual family meals were significantly more likely to respond to treatment than those who had received feedback based on parent report. Occupational therapists are uniquely trained to examine the dynamic transaction between the person (family), environment, and activity that they are engaged in to provide customized feedback or recommendations to support optimal performance. Evaluation of this dynamic interplay is lacking in current health promotion interventions of early childhood; the Mealtime PREP intervention provides a systematic

framework to deliver this feedback.

In our early pilot work, the Mealtime PREP intervention empowered parents from middle to high-income families to increase the frequency of family meals, feel confident about managing daily meals, and change daily mealtime routines. However, this study focused on children with Sensory Food Aversions and our convenience sample was homogenous and lacked diversity. Because of the complex barriers faced by low-income families, further investigation is required to determine how to best serve these families. Despite economic, attitudinal and accessibility limitations, longitudinal surveillance of this population has revealed that positive parenting interventions to prevent behavioral issues and aggression appear to have a protective capacity against obesity. While not the primary intent of these interventions, this evidence provides a signal that early intervention focused on parent education, empowerment, and behavior change is a promising approach for obesity prevention. While we are not able to test whether the Mealtime PREP intervention effectively prevents obesity over a 12-week period, the purpose of this trial is to gather data to optimize our approach and meet the needs of low-income families for future trials with long-term follow-up.

**Study Objectives:** The purpose of this pilot project is to trial the Mealtime PREP intervention program with a sample of low-income families.

Specifically, we aim:

1. To examine the feasibility and acceptability of the Mealtime PREP intervention among low-income families with a preschooler.
2. To estimate the effects of Mealtime PREP on dietary variety, nutrition, and mealtime behaviors of low-income preschoolers.

**Study Design& Methods:** We plan to use a prospective, repeated-measures study design with data collection occurring at baseline, 6 weeks (post-intervention), and 12 weeks (follow-up). Twenty low-income families with a preschooler will be recruited from waiting rooms and/or staff referral at local WIC, Head Start, and pediatric primary care offices. Interested parents will undergo basic screening procedures (i.e. providing responses to screening questions to determine eligibility) prior to being consented to participate in the study.

After eligibility has been confirmed, interested parent participants will undergo the consent process with a trained research assistant and/or the principal investigator in the home environment or an agreed upon alternative in the community. Following informed consent, baseline assessments (including video-recording a typical child meal) will take place. If the child meal is of average length (approximately 20 minutes), this session will last approximately 60-90 minutes. Additionally, they will be asked to complete a 3 day food diary where they log their child's food intake for three days.

Trained research interventionists will then schedule six weekly sessions to take place in the family home or an agreed upon alternative in the community. Each session will last approximately one-hour and will include didactic and practice portions with the therapist demonstrating techniques during a child meal and providing feedback as needed. The entire session will be video-recorded by the interventionist.

Mealtime PREP – Parent Experience: Parents are trained to deliver each intervention component during mealtimes using a step-wise, behavioral activation approach. The parent-

training prong of the Mealtime PREP intervention incorporates four active ingredients of behavioral activation (1. skills training; 2. goal-setting; 3. activity scheduling; and 4. activity monitoring) to help parents build a family meal routine that is enriched with techniques to promote child nutrition (Figure 1). Trained research interventionists with experience in pediatric occupational therapy will lead six weekly parent-training sessions in the home. During each session a new intervention component (e.g. Family Meals, Positive Reinforcement) to promote healthy child feeding habits will be introduced and parents will be provided direct feedback while practicing new skills during a child meal. Parents will work with the therapist to set-up a plan and set a goal to practice delivering intervention components in the home between parent-training sessions.

**Mealtime PREP – Child Experience:** The child-focused prong of the Mealtime PREP intervention embeds positive reinforcement of healthy eating habits and repeated exposure to targeted healthy foods into a consistent family meal routine. Parents will incorporate intervention components (Family Meals, Positive Reinforcement, Food Exploration and Food Play) into the child's routine sequentially, as they are trained to deliver them. In essence, the parent will provide a predictable family meal routine, encourage active child participation, reward healthy eating habits and redirect unhealthy behaviors to acceptable alternatives. Parents will also model healthy eating habits and demonstrate various ways to learn about healthy foods using exploration and play. The intervention will be customized to accommodate a variety of environments, address unique family barriers and incorporate child-centered play.

Trained research assistants and/or the principal investigator will conduct follow-up assessments within two weeks of intervention completion and approximately 12 weeks following baseline. Each assessment session is predicted to last approximately 60-90 minutes. They will also be provided with a 3-Day Food Diary and Self-addressed envelope at each of these sessions.

Primary outcomes include:

3-Day Food Diary (Caregiver Reported) Child Intake and Variety of Healthy Foods Preferred method of dietary assessment because of a balance between validity and burden. Includes all food consumed and approximate servings for 3 days.

NutriSTEP and NutriSTEP Toddler Child Risk of Nutritional Deficiency 17 item, validated screen for young children (1–5 years) that categorizes risk of nutritional deficiency into 3 categories (low, moderate, and high).

Parenting Stress Inventory-Short Form Parental Stress Validated tool to assess and categorize parental stress.

**Eligibility Criteria:** Families will be eligible for participation if they have a child in the age range of two to five years old and reside in a low-income household (as specified by income within the range to qualify for WIC services). Parent participants will be eligible for participation if they are > 18 years old, speak English, read at a 6th grade level, and agree to deliver intervention during daily meals.

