## Statistical Considerations

**Data Analysis:** Specific Aim 1: To examine the feasibility and acceptability of the Mealtime PREP intervention among low-income families, we will rely on descriptive statistics (raw scores, frequencies, and percentages) to determine if each benchmark of feasibility has been met. Specific Aim 2: To estimate the effects (child dietary variety, nutrition risk, parental stress) of the

Mealttime PREP intervention, we will calculate effect sizes (Cohen's  $d$ ) based on mean scores of the sample at each time point. Effect sizes will be used to predict effects among low-income families and calculate appropriate sample sizes for future studies. For each outcome of interest, we will run exploratory paired t-tests ( $\alpha = .05$ ) using IBM SPSS Statistics, Version 24. If the data is not normally distributed or if there are outliers upon data exploration, we will switch to equivalent non-parametric tests (e.g. Wilcoxon Signed-Rank). These results will serve as a signal of the ability of this intervention to change behavior over time.

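### Does timing the post-intervention visit from completion and the 12-week visit from baseline let the two time points run together?

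*Combined protocol and SAP*

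**What the plan says.** Study Design & Methods in the combined protocol and SAP gives a nominal schedule: "data collection occurring at baseline, 6 weeks (post-intervention), and 12 weeks (follow-up"). After baseline, interventionists "will then schedule six weekly sessions to take place in the family home" or an agreed alternative.

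The same section, after the description of the child experience, gives the working rule for the follow-up visits. Staff will "conduct follow-up assessments within two weeks of intervention completion and approximately 12 weeks following baseline". For the diary, families at follow-up are told: "They will also be provided with a 3-Day Food Diary and Self-addressed envelope at each of these sessions".

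On content, the parent-experience text says: "During each session a new intervention component (e.g. Family Meals, Positive Reinforcement) to promote healthy child feeding habits will be introduced". Nothing is said about a missed session.

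Statistical Considerations computes Cohen's d "based on mean scores of the sample at each time point" and adds: "For each outcome of interest, we will run exploratory paired t-tests". It does not name the pairs of time points to be tested. The effect sizes are also meant to inform sample sizes for later studies.

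**The concern.** The two follow-up visits are counted from different origins. Completion depends on how quickly a family gets through its sessions; week 12 is fixed from baseline. The text gives no window for the first session, no make-up rule, no latest date for the post-intervention visit, no tolerance around week 12 and no minimum interval. Since each session brings a new component, making up a missed one is a natural choice, and doing so pushes the post-intervention visit towards week 12.

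For a late family, the values labelled 6 weeks and 12 weeks could then describe nearly the same moment, and time since the last session at week 12 would vary between families. If the 12-week effect size were read as persistence after treatment, or the post-intervention one as an exact six-week value, it would be mislabelled for those families. The figures are intended for planning later trials, so the label matters. The protocol's own background describes a population facing considerable barriers, so some slippage is foreseeable.

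**Working it through.** **Inputs from the documents.** Six weekly sessions; post-intervention visit 0 to 2 weeks after completion; second follow-up visit at about week 12 from baseline; 20 families in a single group.

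**Assumptions (not in the documents).** First session g = 0 or 1 week after baseline; m = weeks of slippage; completion = sixth session; second follow-up visit exactly at week 12.

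**Formulas.**
- Week of sixth session: L = g + 5 + m.
- Post-intervention window: L to L + 2.
- Gap to week 12: (5 − g − m) to (7 − g − m).
- Weeks since the last session at week 12: 7 − g − m.

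**Nominal schedule reproduced.** With m = 0, g = 1 gives L = 6, a window of weeks 6 to 8 and a gap of 4 to 6 weeks. With g = 0, the window is weeks 5 to 7 and the gap 5 to 7 weeks. Both windows contain the stated 6 weeks, so the nominal schedule and the working rule agree for families on time.

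**Late families, sessions made up, g = 1.**

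| Slippage m (weeks) | Post-intervention window (weeks) | Gap to week 12 (weeks) | Weeks since last session at week 12 |
|---|---|---|---|
| 0 | 6–8 | 4–6 | 6 |
| 2 | 8–10 | 2–4 | 4 |
| 3 | 9–11 | 1–3 | 3 |
| 4 | 10–12 | 0–2 | 2 |
| 5 | 11–13 | −1 to 1 | 1 |

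With g = 0, each row is reached one week of slippage later. At m = 4, a visit on the day of completion still leaves two weeks.

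**How many families.** The documents give no attendance rate. Assume each weekly appointment is kept independently with probability p and missed sessions are made up. Then m is negative binomial with 6 successes:

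P(m ≥ 4) = 1 − p⁶[1 + 6q + 21q² + 56q³], with q = 1 − p.

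- p = 0.9: 0.008, × 20 = 0.2 families.
- p = 0.8: 0.086, × 20 = 1.7 families.
- p = 0.7: 0.270, × 20 = 5.4 families.

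**If sessions are not made up.** The sixth weekly appointment stays where it was, so the gap remains 4 to 6 weeks (g = 1). Counting every family with fewer than six sessions as lacking a completion date would overstate the gap in the text: a family that misses the third session but attends the sixth has a clear end date. Only families who miss the sixth appointment lack that date: 1 − p = 0.1, 0.2 and 0.3, × 20 = 2, 4 and 6 families. For them, the nominal 6 weeks remains as a fallback.

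**Which planned results depend on the gap.**
- Baseline against post-intervention: uses baseline and the completion-anchored visit. The gap does not enter.
- Baseline against 12 weeks: uses two visits on the baseline clock. The gap does not enter.
- Post-intervention against 12 weeks: depends on the gap. Statistical Considerations does not specify this contrast.

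**The case for a change.** The best case for a change is that it would be cheap and the timing is loose. The analysis section names no pairs, so a paired test of post-intervention against 12 weeks is not excluded, and the background predicts that changes will persist, which invites that reading. Earlier pilot work was in middle- to high-income families, so its attendance may not carry over. The diary is a primary outcome with no stated return date.

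The different origins, the absent minimum gap and the incomplete definition of completion are all real, and at attendance near 0.7 with make-up sessions the number of late families is not trivial. The rest carries less weight. The prediction of persistence is background, and no analysis is attached to it. No direction of bias, change in Cohen's d or change in a future sample size has been shown. The diary is handed out at both follow-up visits, so a similar delay moves both and does not by itself narrow the gap.

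The one remedy that would keep the visits apart, a latest week for the post-intervention visit, means assessing some late families before their last session. The post-intervention mean would then mix fully and partly treated families. Timing that visit from completion avoids this, at the price of a variable gap. Either choice is defensible.

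**Conclusion.** No change is needed. Followed as written, the plan gives interpretable estimates of change from baseline to the end of the intervention and from baseline to about week 12. Near-coincidence of the visits requires make-up sessions and roughly four weeks of slippage with a first session at week 1 (five weeks if the first session is at week 0). That would be about 0.2, 1.7 or 5.4 of 20 families at assumed attendance of 0.9, 0.8 or 0.7; the true share cannot be estimated from the documents. Without make-up sessions the gap stays as planned.

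What is missing is operational detail. A study team would take the sixth session, or the last one a family attended, as completion, and could describe visit timing from its own dates without altering any estimate. Choosing completion over a fixed calendar date for the post-intervention visit is a fair trade-off in an exploratory 20-family pilot. This conclusion rests on the 12-week value being read as status 12 weeks after baseline. A claim of persistence for a fixed time after treatment would need more than this plan sets out, and the plan does not define one.

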## Statistical Considerations

**Data Analysis:** Specific Aim 1: To examine the feasibility and acceptability of the Mealtime PREP intervention among low-income families, we will rely on descriptive statistics (raw scores, frequencies, and percentages) to determine if each benchmark of feasibility has been met. Specific Aim 2: To estimate the effects (child dietary variety, nutrition risk, parental stress) of the

Mealttime PREP intervention, we will calculate effect sizes (Cohen's  $d$ ) based on mean scores of the sample at each time point. Effect sizes will be used to predict effects among low-income families and calculate appropriate sample sizes for future studies. For each outcome of interest, we will run exploratory paired t-tests ( $\alpha = .05$ ) using IBM SPSS Statistics, Version 24. If the data is not normally distributed or if there are outliers upon data exploration, we will switch to equivalent non-parametric tests (e.g. Wilcoxon Signed-Rank). These results will serve as a signal of the ability of this intervention to change behavior over time.

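### Does Aim 1 need changing because only parents who agree to daily-meal delivery can enter, and because no benchmark, unit or denominator is listed?

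*Combined protocol and SAP*

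**What the plan says.** Study Objectives gives the first aim as "To examine the feasibility and acceptability of the Mealtime PREP intervention among low-income families with a preschooler". Study Design & Methods sets the size: "Twenty low-income families with a preschooler will be recruited". It also describes entry: "Interested parents will undergo basic screening procedures (i.e. providing responses to screening questions to determine eligibility) prior to being consented". Eligibility Criteria adds, among the conditions for parents, that they "agree to deliver intervention during daily meals". After consent and baseline assessment, "Trained research interventionists will then schedule six weekly sessions".

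Under Statistical Considerations, Data Analysis, Aim 1 is handled by raw scores, frequencies and percentages, used "to determine if each benchmark of feasibility has been met". The document does not say what the benchmarks are, what is counted, or out of how many. It names no acceptability measure. The three listed primary outcomes (food diary, nutrition-risk screen, parenting stress) correspond to the Aim 2 effects. No section mentions a count of parents approached, screened, unwilling or consented.

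**The concern.** Scientific Background names the barrier the intervention must overcome: "parents of young children report difficulty incorporating new skills into established daily routines". If willingness to take this on at daily meals is a condition of entry, some families for whom the barrier is decisive never join the 20. A percentage among consented families then answers a narrower question than Aim 1 asks. The protocol says the trial is meant to inform later trials in low-income families, and those trials would want to know how many such families take the programme up.

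The second worry is the yes/no verdict on each benchmark. With no unit or denominator stated, the verdict could depend on whether families or sessions are counted, or on whether the base is screened, consented or retained families. A reader of this document alone cannot confirm that those choices were fixed before the data were seen.

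**Working it through.** There is no planned figure to reproduce. The 20 families come without a power or precision statement, and Aim 1 has no numeric benchmark. The only inputs from the document are 20 families and six sessions per family; every other count below is an assumption used for illustration.

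**Selection.** Let s be the share of otherwise eligible, interested parents who do not agree to daily-meal delivery (assumed 10% to 50%), and p the proportion of consented families who complete. Among all such parents the proportion is p × (1 − s). With p = 16/20 = 80%:

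| s | Calculation | Result |
|---|---|---|
| 10% | 0.80 × 0.90 | 72% |
| 20% | 16/25 | 64% |
| one third | 16/30 | 53% |
| 50% | 16/40 | 40% |

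This is an identity: uptake (1 − s) times completion given uptake (p). It shows how the two combine but does not show that s is large here.

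**Unit.** 20 × 6 = 120 sessions. If T sessions are attended, the number of families attending all six lies between max(0, T − 100) and floor(T/6), because 20 families at five sessions each make 100.
- T = 96 (80% of sessions): 0 to 16 families.
- T = 108 (90%): 8 to 18 families.

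Unit can therefore matter, if session attendance is a benchmark at all. The document does not say that it is.

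**Denominator.** Follow-up diaries are handed out for return ("3-Day Food Diary and Self-addressed envelope at each of these sessions"). If 14 came back, that is 14/20 = 70% of consented families, against 14/19 = 74% to 14/16 = 88% of retained families if 16 to 19 were retained. The diary is listed as a primary outcome and is nowhere named as a feasibility benchmark.

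**Precision.** 16/20 has an exact 95% interval of 56% to 94%. A hypothetical benchmark of at least 16 of 20 would be met with probability 0.24, 0.63 and 0.96 at true rates of 70%, 80% and 90%. This is the ordinary limit of 20 families. Printing an interval beside a benchmark would not alter whether the benchmark was met.

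**Reading the entry rule against the barrier.** Eligibility Criteria asks for agreement beforehand, not demonstrated ability. A parent who agrees and then cannot fit the skills into the day is enrolled and counted, and this is the difficulty that Scientific Background describes. The goal-setting, activity monitoring and feedback in the intervention address it after entry. Only parents unwilling at the outset are lost, and they would not be expected to consent to a parent-delivered programme even if the criterion were deleted.

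**The case for a change.** The strongest case for a change is that feasibility is the first aim, that it is worded for low-income families in general, and that the earlier pilot work was in middle- to high-income families, so transfer to this population is the reason for the trial. A tally of parents who decline the daily-meal condition would cost almost nothing, and so would a list of the benchmarks with their denominators.

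Much of this stands as fact. The document lists no benchmarks and no acceptability measure, it plans no refusal count, and Aim 1 results will describe families who had agreed beforehand. What does not stand is the step from there to a fault in the plan. No stated rule or figure is shown to be wrong. The phrase about each benchmark presupposes a list, which may already cover uptake and denominators. A tally of screened parents would still miss those approached in waiting rooms or referred by staff who showed no interest, so it would not give the population uptake that the argument calls for. Nor does the document say that agreement to daily-meal delivery is one of the screening questions; that is only a plausible reading.

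**Conclusion.** The concern does not call for a change to the plan. The entry condition is normal for an intervention that parents deliver, and feasibility among enrolled families is a legitimate question for a 20-family pilot. The missing unit and denominator are details that analysts can settle sensibly: consented families as the base for what happens after consent, uptake and completion kept as separate figures, and conclusions worded for families who agreed to take part.

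The possible size is real but unquantified. The drop from 80% to between 72% and 40% rests wholly on an assumed 10% to 50% of parents not agreeing, and the unit and retention examples rest on measures the document does not name as benchmarks. The reach is small: no go/no-go decision is tied to Aim 1, and Data Analysis takes future sample sizes from the Aim 2 effect sizes.

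This conclusion assumes that a benchmark list exists outside the public document, as the wording implies. If none was set in advance, a met/not-met verdict would have no basis and Aim 1 could be read only as description. The document gives no evidence that this is so.

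### Could Cohen's d and the paired tests rest on different families, and does the plan need to redefine d for that reason?

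*Combined protocol and SAP*

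**What the plan says.** Under Statistical Considerations, Data Analysis, Specific Aim 2, d is computed "based on mean scores of the sample at each time point". The next step is the test: "For each outcome of interest, we will run exploratory paired t-tests", with a switch to a signed-rank test if the data are non-normal or contain outliers. On the use of d the plan states: "Effect sizes will be used to predict effects among low-income families and calculate appropriate sample sizes for future studies".

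The Study Design & Methods section plans 20 families in one group, assessed at baseline, 6 weeks and 12 weeks. On the two later assessments it says: "They will also be provided with a 3-Day Food Diary and Self-addressed envelope at each of these sessions". The baseline diary is likewise a three-day log, requested in addition to the baseline session.

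The documents give no analysis set, missing-data rule, expected dropout, SD, correlation between visits or divisor for d.

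**The concern.** A paired t-test or signed-rank test drops any family that lacks one of its two values. Nothing ties d to those same families. If d takes the baseline mean of everyone and the later mean of those who remain, it mixes real change with a change in who is being averaged.

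Missing values are foreseeable. A family can attend a visit and never post the diary. If each later value is missing independently with an assumed probability of 5%, 10% or 20%, the chance that all 20 families supply it is 0.95^20 = 36%, 0.90^20 = 12% or 0.80^20 = 1%.

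The stake is the next trial, since d is meant to size it. Suppose d on pairs is 0.50, 4 of 20 families are missing, and completers differ from non-completers at baseline by 0.5 SD in either direction. The literal d is then 0.50 ± (4/20) × 0.5, that is 0.40 to 0.60. A future two-arm trial (two-sided 5%, 80% power) would be planned with 99 to 44 per arm instead of 63.

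**Working it through.** The plan states no figure to reproduce. Only the 20 families and the three visits come from the documents. Dropout, the correlation r between visits, the loss mechanism and the true d are assumptions. Differences are in baseline SD units.

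**1. Size of the mismatch.** If every family has a baseline value, then

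(later mean of stayers − baseline mean of all) − (paired change of stayers) = baseline mean of stayers − baseline mean of all.

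With full retention this is zero. With m of 20 retained at random its mean is zero and its SD is √(1/m − 1/20):

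- m = 18: 0.075; chance of a gap above 0.1 is 18%
- m = 16: 0.112; 37%
- m = 14: 0.146; 49%

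The identity fails if baseline diaries are missing too, which the plan's procedure makes possible.

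**2. Does the mismatch make the literal version less accurate under random loss?** With equal SDs at both visits, the variances are:

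- literal difference: 1/m + 1/20 − 2r/20
- paired change: 2(1 − r)/m

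At r = 0.5 both reduce to 1/m, giving a standard error of 0.236, 0.250 and 0.267 for m = 18, 16 and 14. With m = 14, the literal version is slightly more precise at r = 0.3 (0.302 against 0.316) and slightly less precise at r = 0.7 (0.227 against 0.207). So the 18%, 37% and 49% measure disagreement between two estimates of similar precision, not error in one of them.

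**3. Informative loss.** This was simulated with no true change, 30% loss and a logistic slope of 0.7 per SD, where families with low values of the driver leave more often. Bias at r = 0.5 / r = 0.7:

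| Loss depends on | Literal d | Paired change |
|---|---|---|
| Baseline value | +0.10 / +0.14 | −0.10 / −0.06 |
| Stable family trait | +0.14 / +0.16 | 0.00 / 0.00 |
| Later value | +0.19 / +0.19 | +0.10 / +0.06 |
| Change | +0.10 / +0.07 | +0.19 / +0.15 |

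At 10% loss the literal bias is +0.03 to +0.07.

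**4. Consequence for planning.** Take a true d of 0.40, r = 0.5, a paired design, two-sided 5% and 80% power; 52 pairs are needed. Adding the biases from step 3:

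- Loss by baseline: the literal d of 0.50 plans 34 pairs (62% power at 0.40); the paired d of 0.30 plans 90.
- Loss by trait: the paired d stays at 0.40 and plans 52; the literal d is too large.
- Loss by later value: the literal d of 0.59 plans 25 (48% power); the paired d of 0.50 plans 34.
- Loss by change: the literal d of 0.50 plans 34; the paired d of 0.59 plans 25 (48% power).

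**5. The divisor.** The SD of change in place of the baseline SD multiplies d by 1/√(2(1 − r)): 0.85, 1.00 or 1.29 at r = 0.3, 0.5 or 0.7. A d of 0.40 on the baseline SD therefore means 71, 52 or 32 pairs. Fixing the baseline SD in the plan would not settle this, because the next sample size also needs r or the SD of change.

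**The case for a change.** The best argument for a change is that d is the quantity carried forward, complete data are unlikely, and one sentence tying d to the paired families would cost nothing. In the table the paired change has the smaller bias in five of the eight cells, an equal-sized bias in one and a larger bias in two. A sponsor who already meant pairs would lose nothing by saying so.

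Part of this stands. The term is undefined, the divisor is unnamed, and pairs are the more natural choice. It does not make the plan wrong, because the sample may just as well mean one fixed set of families. It does not show that readers would be misled either, since nothing suggests that the n at each visit will go unreported. The advantage of pairs rests on an assumed loss mechanism and reverses when families leave because of how their child changed.

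A mixed model added as a sensitivity analysis would not resolve this. Under the same assumptions, a likelihood-type estimate is unbiased when loss depends on baseline, but at r = 0.5 it is biased by +0.07 for trait-driven loss, where the paired change has none, and by +0.15 for loss by later value, against +0.10 for pairs.

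**Conclusion.** No change to the plan follows. The wording leaves open which families and which SD define d, and an analyst who runs the paired tests has the paired means at hand and would most likely use them. If the literal reading were followed, the discrepancy would be zero with full retention and zero on average under random loss. Its SD of 0.07 to 0.15 is well below the 0.24 to 0.27 standard error of either version at r = 0.5. Under informative loss either version can mislead the next sample size, and which does worse depends on a mechanism the documents do not describe.

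Naming the SD and giving n for each contrast are ordinary parts of reporting an effect size and can be done when the results are written up. These conclusions rest on assumed dropout of 10% to 30%, r of 0.3 to 0.7 and a logistic slope of 0.7, and on complete baseline data. The setting is a single-group pilot of 20 families whose tests the plan itself calls exploratory.
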